9.6.2 Laboratory Test Results

The analyses of **key** safety laboratory endpoints will include summary statistics at selected time points by treatment group. Shifts in grades of safety laboratory parameters from baseline to worst post-baseline value for select blood chemistry analytes (albumin, creatinine, **total bilirubin**) and **hematology analytes (hemoglobin, white blood cells (WBC) count, platelet count, absolute neutrophil count)** will be tabulated by treatment group.

In addition, a summary of potential hepatotoxicity by Hy's Law will also be tabulated (the criteria is defined as AST or ALT > 3 times upper limit of normal (ULN), total bilirubin > 2 times ULN, and alkaline phosphatase < 2 times ULN assessed within 7, 14 and 28 days).

9.6.3 Vital Signs

The analyses of vital signs **parameters of systolic/diastolic blood pressure, heart rate, respiratory rate, and temperature** will include summary statistics at selected time points by treatment group.

Shifts in ECOG performance status scores between baseline and each post-baseline assessment will be tabulated by treatment group.

9.6.4 Electrocardiogram

The electrocardiogram (ECG) measurements from this clinical study were performed as per standard of care for routine safety monitoring, rather than for purposes of assessment of potential QT interval corrected (QTc) effect. Because these evaluations may not necessarily be performed under the rigorous conditions expected to lead to

meaningful evaluation of QTc data; neither summaries nor statistical analyses will be provided, and these data would not be expected to be useful for meta-analysis with data from other trials.

9.6.5 Antibody Formation

The number and percentage of subjects who develop anti- romiplostim and anti-TPO antibodies (binding and if positive, neutralizing) at any time will be tabulated by treatment group.

The week 1 baseline antibody sample will be obtained before the first administration of investigational product. Antibody samples will assess safety, development of binding and neutralizing antibodies to romiplostim and the potential to bind to endogenous TPO

9.6.6 Exposure to Investigational Product

The duration of investigational product exposure, cumulative dose, average weekly dose, most frequently received dose, minimum dose, and maximum dose will be summarized using descriptive statistics.

In addition, number and percentages of dose reduction, delays, and omission with reasons will be summarized by treatment group. **Missing visits due to COVID-19 will be summarized.**

9.6.7 Exposure to Other Protocol-required Therapy

The number and percentage of subjects receiving each chemotherapy agent, the number of chemotherapy cycles received, and the number and percentage of dose reductions, dose delays, and doses omitted (withheld) will be summarized by treatment group.

9.6.8 Exposure to Concomitant Medication

The number and proportion of subjects receiving concomitant medications will be summarized by preferred term for each treatment group as coded by the World Health Organization Drug (WHO DRUG) dictionary.

[figure not shown]
9.7 Other Analyses

The number and percentage of subjects who experience an event will be tabulated for each of the following endpoints: myelodysplastic syndromes and secondary malignancies (including progression from myelodysplastic syndrome to acute myeloid leukemia). In addition, Kaplan-Meier curves and hazard ratios between treatment group with 95% CIs will be calculated for myelodysplastic syndrome free time (censor at death), myelodysplastic syndrome free survival time (consider death an event), secondary malignancy free time (censor at death), and secondary malignancy free

survival time (consider death an event). These analyses will be summarized by treatment group using the safety analysis set.

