#### **10.3.2.4       Other Analyses**

The number and percentage of subjects who experience an event will be tabulated for each of the following endpoints: myelodysplastic syndromes and secondary malignancies (including progression from myelodysplastic syndrome to acute myeloid leukemia). In addition, Kaplan-Meier curves and hazard ratios with 95% CIs will be calculated for myelodysplastic syndrome free time (censor at death), myelodysplastic syndrome free survival time (consider death an event), secondary malignancy free time (censor at death), and secondary malignancy free survival time (consider death an

event). These analyses will be summarized by treatment group using the safety analysis set.

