Achieving a platelet count $\geq 100 \times 10^9/L$ at any time after study day 1, up to and including the date of the week 4 visit (ie, 7 days after the third planned dose of investigational product). if a platelet transfusion occurred during the 7 days preceding a platelet count, then that platelet count will not be considered as achieving the endpoint even if it is $\geq 100 \times 10^9/L$. Subjects who have no platelet counts during this period will be considered as not achieving achieved a platelet count $\geq 100 \times 10^9/L$. For subjects who never received IP, the subjects are considered as not achieving a platelet count $\geq 100 \times 10^9/L$. Weeks with no platelet count measurements (missing data) are considered as not achieving a platelet count $\geq 100 \times 10^9/L$.

Endpoints: Secondary (safety) – Myelodysplastic Syndromes (MDS) Free Time

Myelodysplastic syndromes (MDS) free time is defined as the time from the first dose of IP to the first occurrence of MDS. Subjects who have not had an MDS event will be censored at their last contact date or death date, whichever is later.

It is calculated as:

Date of first occurrence of MDS or censoring date – the date of the first dose of IP + 1.

MDS events will be identified using the narrow search of myelodysplastic syndromes (SMQ), using the MedDRA version **25.1** or later available at the time of the analysis.

Endpoints: Secondary (safety) – Myelodysplastic Syndromes (MDS) Free Survival Time

MDS free survival time is defined as the time from the first dose of IP to the first occurrence of MDS or death, whichever is earlier. Subjects who have not had an MDS event and have not died will be censored at their last contact date. It is calculated as:

Date of first occurrence of MDS, death or censoring – the date of the first dose date of IP + 1.

MDS events will be identified using the narrow search of myelodysplastic syndromes (SMQ), using the MedDRA version **25.1** or later available at the time of the analysis.

Endpoints: Secondary (safety) – Secondary Malignancy Free Time

[figure not shown]
Secondary malignancy free time is defined as the time from the first dose of IP to the onset of a secondary malignancy. Subjects without an event will be censored at their last contact date or death, whichever is later. It is calculated as:

Date of onset of secondary malignancy or censoring – the date of the first dose IP + 1.

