9.1 General Considerations

Continuous variables will be summarized descriptively by the n, mean, standard deviation, median, Q1 (25th percentile), Q3 (75th percentile), minimum, and maximum. The confidence interval and standard error for the mean will also be summarized for efficacy variables that are continuous. Categorical variables will be summarized descriptively by the number and percentage in each category. Missing values will be shown as a separate category. The confidence interval will also be summarized for dichotomous efficacy variables.

Time to event variables will be summarized with hazard ratios, Kaplan-Meier curves, Kaplan-Meier quartiles, the number of subjects at risk, the number of subjects censored, and the number of subjects with events.

Where confidence intervals are provided, these will be 2-sided at the 95% level, unless otherwise specified.

The primary efficacy endpoint will be compared between the romiplostim and placebo groups at the significance level of 0.05 using a 2-sided test. If statistical significance is achieved for the primary endpoint in favor of romiplostim, **the following secondary efficacy endpoints will be tested using a fixed sequence hierarchical testing procedure to control the family-wise Type I error rate below 2-sided 0.05 level. The family of hypotheses is ordered as follows:**

- the depth of platelet count nadir from the start of the first on-study chemotherapy cycle through the end of the treatment period
- the time to first platelet response, defined by platelet count $\geq 100 \times 10^9/L$, in the absence of platelet transfusions during the preceding 7 days.
- the duration-adjusted event rate of \geq grade 2 bleeding events as assessed per CTCAE version 5.0 grading scale
- overall survival
- platelet transfusion(s) during the treatment period
- achieving platelet count $\geq 100 \times 10^9/L$ at any time after study day 1 to week 4 (ie, 7 days after the planned third dose of investigational product) in the absence of platelet transfusions during the preceding 7 days

Starting with the hypothesis of platelet count nadir, if any null hypothesis in the sequence is rejected at a 2-sided significance level of 0.05, then the subsequent hypothesis will be tested; if any null hypothesis is accepted, then the subsequent hypotheses will not be tested.

Summary statistics without formal testing will be provided for other endpoints.

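### Add cumulative incidence curves for MDS and secondary malignancy: the planned Kaplan-Meier curves censor deaths and overstate absolute risk if read as such

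*SAP*

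**What the plan says.** SAP 9.7 and Protocol 10.3.2.4 describe four time-to-event endpoints in two pairs. For MDS the pair is "myelodysplastic syndrome free time (censor at death), myelodysplastic syndrome free survival time (consider death an event". For secondary malignancy it is "secondary malignancy free time (censor at death), and secondary malignancy free survival time (consider death an" event. The SAP's sentence begins "Kaplan-Meier curves and hazard ratios between treatment group with 95% CIs will be calculated for myelodysplastic syndrome free time (censor at death", and the same curves and hazard ratios are planned for all four, by arm, in the safety analysis set.

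SAP Section 5 (Definitions) makes the censoring operational. For MDS-free time: "Subjects who have not had an MDS event will be censored at their last contact date or death date, whichever is later". For secondary-malignancy-free time: "Subjects without an event will be censored at their last contact date or death, whichever is later". The same section defines last contact as the latest date on which the subject is known to be alive, so a subject who dies without the event is censored at death.

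SAP 9.7 opens with a crude summary: "The number and percentage of subjects who experience an event will be tabulated for each of the following endpoints". These endpoints lie outside the fixed testing sequence; SAP 9.1 states "Summary statistics without formal testing will be provided for other endpoints". Neither document mentions a cumulative incidence function or any other competing-risk method.

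**The concern.** Death is a competing event for both outcomes. The Kaplan-Meier estimate with deaths censored describes how event times would look if nobody died first. Its complement (1-KM) is therefore not the proportion of these patients who develop MDS or a second malignancy by a given time.

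The other planned outputs do not supply that proportion over time:

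- The free-survival endpoints count death together with MDS or malignancy. Where deaths far outnumber the events of interest, the curve mainly shows mortality.
- The crude percentage is not inflated but has no time axis, and Protocol 5.3.2 expects study durations of about 14 to 50 months per subject.

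The death-censored curve is thus the only planned display that isolates MDS or malignancy over time, and it is open to being read as absolute risk. Both outcomes are listed secondary safety endpoints (Protocol 4.1, SAP 2.1). Substantial mortality is plausible, because pancreatic cancer is included and stage does not restrict eligibility, although no rate is given.

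**Working it through.** The plan gives no figure on this point to reproduce. All rates below are assumptions.

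**Formulas.** With constant cause-specific hazards m (event) and d (death), at time T in years:

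- 1-KM with deaths censored = 1 − exp(−mT)
- Cumulative incidence with death competing = m/(m+d) × [1 − exp(−(m+d)T)]

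**Check 1: m = 0.01 per year, d = 0.4 and 0.6 per year.** These death hazards correspond to 1 − exp(−0.4) = 33% and 1 − exp(−0.6) = 45% dying per year.

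- T = 3: 1-KM = 1 − exp(−0.03) = 2.96%.
  - d = 0.4: (0.01/0.41) × [1 − exp(−1.23)] = 1.73%, ratio 1.7.
  - d = 0.6: (0.01/0.61) × [1 − exp(−1.83)] = 1.38%, ratio 2.1.
- T = 1: 1-KM = 1.00%, against 0.82% and 0.75%, ratios 1.2 and 1.3.

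**Check 2: wider grid.** Median survival is 9 to 60 months, with d = ln 2 / median. The yearly event probability r is 0.5% to 2%, with m = −ln(1 − r). Horizons of 14 and 50 months match the ends of the study duration in Protocol 5.3.2; 36 months lies between. Results for r = 1%:

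| Horizon (months) | Median survival (months) | 1-KM | Cumulative incidence | Ratio |
|---|---|---|---|---|
| 14 | 60 | 1.17% | 1.08% | 1.08 |
| 14 | 9 | 1.17% | 0.71% | 1.63 |
| 36 | 60 | 2.97% | 2.43% | 1.22 |
| 36 | 18 | 2.97% | 1.61% | 1.84 |
| 36 | 9 | 2.97% | 1.01% | 2.94 |
| 50 | 60 | 4.10% | 3.12% | 1.31 |
| 50 | 9 | 4.10% | 1.05% | 3.89 |

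Over the whole grid the ratio runs from 1.08 to 3.91 and the absolute excess from 0.04 to 6.0 percentage points. The ratio hardly depends on the event rate (at 36 months and 9-month median survival: 2.95, 2.94 and 2.92 for r = 0.5%, 1% and 2%). It therefore applies equally to secondary malignancy while that event is rare.

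**Check 3: simulation.** With n = 108, r = 1%, administrative censoring uniform over 14 to 50 months, and estimates at 36 months:

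| Median survival (months) | True incidence | 1-KM | Aalen-Johansen | Crude % |
|---|---|---|---|---|
| 12 | 1.26% | 2.97% | 1.25% | 1.17% |
| 24 | 1.85% | 3.04% | 1.88% | 1.70% |
| 36 | 2.15% | 3.01% | 2.18% | 1.95% |

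Aalen-Johansen recovers the true value. The crude percentage is not inflated.

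**Check 4: comparison between arms.** Take equal event hazards, r = 1%, T = 36 months, median survival 18 months on placebo and a death hazard ratio of 0.8. Then 1-KM is 2.97% in both arms, while cumulative incidence is 1.80% against 1.61%. The death-censored curve reflects the equal event hazards; the cumulative incidence also reflects longer survival. They answer different questions.

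**Expected events.** Multiplying the grid's cumulative incidence by 162 gives about 0.6 to 10 MDS events in both arms together (162 × 0.36% to 162 × 6.16%).

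**The case against.** The strongest defence is that the plan does not ignore death. It labels the two endpoints as death-censored, pairs each with a version that counts death, and tabulates the crude number and percentage first. Death-censored curves are the natural companions of cause-specific hazard ratios, and they are defensible for asking whether the drug changes the rate of MDS. Nowhere does the SAP say that 1-KM will be reported as a risk. Protocol 3.3.3.6 gives a median latency of 3 to 5 years for chemotherapy-related leukemia, so few events should occur on study, and the excess in most scenarios would lie within the sampling error.

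Most of this stands. It is why the curves should be supplemented rather than removed, and why severity is low. It does not remove the gap: no planned output shows absolute risk over time under unequal follow-up. Sparse late events can also make the death-censored curve look worse. As an assumed illustration, a first event with 20 subjects at risk lowers the Kaplan-Meier curve by 1/20 = 5 points. If event-free survival is then 30%, the Aalen-Johansen step is 0.30/20 = 1.5 points.

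**Conclusion.** The point holds for one use of one display: the complement of the death-censored curves, read as absolute risk, is too high whenever deaths occur. The direction is certain. The size (about 1.1 to 3.9 times on the wide grid, 1.7 to 2.1 times at 3 years in Check 1) rests on constant hazards and on event and mortality rates that the documents do not state.

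A reader might infer more, and the documents do not support it:

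- *That the plan as a whole overstates these risks.* The tabulated number and percentage are not inflated.
- *That the hazard ratios are wrong.* With deaths censored they are valid cause-specific hazard ratios.
- *That high mortality is documented.* Any stage is eligible, and no survival assumption is given.
- *That new MDS and secondary malignancy are named key risks of the drug.* Protocol 3.3.3.6 names progression of existing MDS and calls the concern theoretical, and exclusion criterion 204 rules out subjects with MDS. Both outcomes are listed safety endpoints, which is sufficient reason to display them properly.

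No formal test, event count or hazard ratio changes. This is a low-severity presentation point.

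**What to change.** In SAP 9.7:

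- Add Aalen-Johansen cumulative incidence curves by arm for MDS and for secondary malignancy, with death as a competing event, as the display of absolute risk over time.
- Keep the death-censored hazard ratios, labelled cause-specific, and the free-survival analyses as planned.
- State that 1-KM from the death-censored curves will not be reported as absolute risk.

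Record the addition in SAP Section 10, which currently declares no changes, because Protocol 10.3.2.4 carries the same plan as SAP 9.7.

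The cost is a few lines of text and one standard software option. No new data are needed: long-term follow-up already collects vital status, MDS and secondary malignancies (Protocol 5.1).

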9.7.1 Analyses of Pharmacokinetic or Pharmacokinetic/Pharmacodynamic Endpoints

The Clinical Data Interchange Standards Consortium (CDISC) Analysis Data Model (ADaM) standard will be adopted to create the Analysis Dataset for Pharmacokinetics Concentrations (ADPC). The ADPC dataset includes the following variables: 1) subject level information (eg., subject ID, country, planned treatment, actual treatment received, population flags); 2) PK variables (eg., concentration, actual and scheduled PK sampling time); 3) Dosing variables (eg., planned and actual dose(s), start time, stop time and duration of drug infusion, time relative to first infusion start); 4) Physical measurement variables (eg., demographics, selected baseline characteristics and laboratory measurements) and 5) Miscellaneous variables (eg., study specific variables). The pharmacokinetic analysis will be carried out for PK analysis set.

10. Changes From Protocol-specified Analyses

There are no changes to the protocol-specified analyses.

11. Literature Citations / References

Collett D. Modeling Survival Data In Medical Research, Second Edition. Chapman and Hall, Boca Raton. 2003

Shapiro, S. S., and Wilk, M. B. (1965), An analysis of variance test for normality (complete samples), *Biometrika* 52, 591–611.

Van Elteren PH. "On the Combination of Independent Two-Sample Tests of Wilcoxon." *Bulletin of the International Statistical Institute* 1960;37:351–361.

12. Data Not Covered by This Plan

Further analyses of pharmacokinetic or Pharmacokinetic/Pharmacodynamic endpoints, [REDACTED]

[REDACTED]

[REDACTED]

13. Appendices

Appendix A. Code Fragment for Andersen-Gill Model

Duration adjusted bleeding event (Andersen-Gill Approach):

- K is strata for tumor type
- J is strata for baseline platelet count
- Tstart is time of the (k-1) recurrence for visit = k, or the entry time 0 if visit = 1, or the follow-up time if the (k-1) recurrence time does not occur
- Tstop is time of the kth recurrent if visit = k or follow-up time if the kth recurrence does not occur
- Status is bleeding status of Tstop (1=recurrence and 0=censored)
- txgrp is the treatment group variable:
 - active
 - placebo

PROC PHREG covs(aggregate);

Class J K txgrp;

MODEL (Tstart,Tstop)*Status(0)=Txgrp / ties=efron;

Strata K J;

Id usubjid;

Run;

Appendix B. Handling of Dates, Incomplete Dates and Missing Dates**Imputation Rules for Partial or Missing Start Dates**

The reference date for the following rules is the date of first dose[of study drug].

Start Date		Stop Date						Missing	
		Complete: yyyymmdd		Partial: yyyymm		Partial: yyyy			
		< 1 st dose	≥ 1 st dose	< 1 st dose yyyymm	≥ 1 st dose yyyymm	< 1 st dose yyyy	≥ 1 st dose yyyy		
Partial: yyyymm	= 1 st dose yyyymm	2	1	n/a	1	n/a	1	1	
	≠ 1 st dose yyyymm		2	2	2	2	2	2	
Partial: yyyy	= 1 st dose yyyy	3	1	3	1	n/a	1	1	
	≠ 1 st dose yyyy		3		3	3	3	3	
Missing		4	1	4	1	4	1	1	

1=Impute the date of first dose; 2=Impute the first of the month; 3=Impute January 1 of the year; 4=Impute January 1 of the stop year

Note: Note: If the start date imputation leads to a start date that is after the stop date, then do not impute the start date.

Imputation Rules for Partial or Missing Stop Dates

Initial imputation

- **If the month and year are present, impute the last day of that month.**
- **If only the year is present, impute December 31 of that year.**
- **If the stop date is entirely missing, assume the event or medication is ongoing.**

If the imputed stop date is before the start date, set stop date to missing.

If the imputed stop date is after the death date, impute as death date.

Death Dates, Secondary Malignancy Onset Dates, and MDS Onset Dates

If death/malignancy/MDS year and month are available but day is missing:

- If mmYYYY for last contact date = mmYYYY for death/malignancy/MDS date, set death/malignancy/MDS date to the day after the last contact date or EOS date, whichever occurs first.
- If mmYYYY for last contact date < mmYYYY for death/malignancy/MDS date, set death/malignancy/MDS date to the first day of the death/malignancy/MDS month.

- If mmYYYY for last contact date > mmYYYY for death/malignancy/MDS date, data error and do not impute.

If both month and day are missing for death/malignancy/MDS date or a death / malignancy / MDS date is totally missing, do not impute.

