Subjects will have their first in-clinic LTFU visit 30 (+ 5) days after the last dose of investigational product (Safety Follow-up 1). Subjects will be contacted 30 (+5 days) after the last dose of the last on-study cycle of chemotherapy (up to 3 cycles) to collect adverse event information except for females who are in addition required to come to clinic for a highly sensitive urine **or serum** pregnancy test (Safety Follow-up 2). Subjects will remain in LTFU until the last subject in the trial completes the LTFU visit 1 year after the last dose of investigational product. During the LTFU period, all subjects will be followed by phone or in clinic every 12 weeks (\pm 2 weeks) **from the last dose of investigational product** until the end of study (EOS) visit. All subjects should complete EOS visit up to 2 weeks after the last subject in the trial completes their LTFU visit 1 year after the last dose of investigational product.

During LTFU subjects will be followed for the diagnosis of, or progression to, secondary malignancies (including myeloid malignancies) or myelodysplastic syndromes, as well as vital status and cause(s) of death.

[figure not shown]

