Endpoints: Secondary (safety) – Secondary Malignancy Free Survival Time

Secondary malignancy free survival time is defined as the time from the first dose of IP to the onset of a secondary malignancy or death, whichever is earlier. Subjects without an event will be censored at their last contact date. It is calculated as:

Date of onset of secondary malignancy, death or censoring – the date of the first dose date of IP + 1.

Last Contact Date

The latest date on which a subject is known to alive.

Myelosuppressive Treatment Agents

Myelosuppressive treatment agents are those agents in the on-study chemotherapy regimen that are 5-fluorouracil **or capecitabine and oxaliplatin (plus irinotecan in FOLFIRINOX or FOLFOXIRI) (Oxaliplatin)-based chemotherapy regimen.**

On-study Chemotherapy Regimens

The on-study chemotherapy regimen is the chemotherapy regimen planned to be taken after study day 1. It will be the same chemotherapy regimen taken in the last chemotherapy cycle immediately before study day 1.

Platelet Counts

If there are multiple platelet values performed on a study visit date, the platelet value most immediately prior to **non-IP** administration **will be selected**, as the platelet value for that study visit date. **If no platelet value prior to non-IP administration, the platelet value prior to IP administration will be selected.**

Prior Use of Medication at Baseline

Prior use of medication at baseline means the medication has been administered prior to the start of the current chemotherapy regimen.

Randomization Date

Randomization date is defined as the date the subject is randomized to a treatment group. Per protocol, subjects should initiate IP the same day they are randomized.

Study Day 1

Study day 1 is defined as the randomization date. **If the randomization date and the first IP administration date are the same, then study day 1 is the randomization date for both efficacy and safety analysis.**

If randomization date and subject first IP administration date are different then study day 1 will be derived using first IP administration date.

Study Day

For dates occurring on or after the study day 1 date, study day will be calculated as:

Date of interest - **date of first IP administration** + 1.

For dates occurring before the study day 1 date, study day will be calculated as:

Date of interest - **date of first IP administration.**

Treatment-emergent Adverse Event

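### SAP Appendix B dates MDS and secondary-malignancy onset by a rule that fits only death, so an onset with only the day missing will usually be left undated

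*SAP*

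**What the plan says.** The last block of SAP Appendix B is headed "Death Dates, Secondary Malignancy Onset Dates, and MDS Onset Dates", and its branches make no distinction among the three kinds of date. The block opens with the condition "If death/malignancy/MDS year and month are available but day is missing" and then compares the month of last contact with the month of the event:

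- Same month: "set death/malignancy/MDS date to the day after the last contact date or EOS date, whichever occurs first".
- Last contact in an earlier month: the first day of the event month is used.
- Last contact in a later month: "If mmYYYY for last contact date > mmYYYY for death/malignancy/MDS date, data error and do not impute".

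SAP Section 5 defines last contact date as "The latest date on which a subject is known to alive". It also sets out the endpoint that needs the onset date: "Myelodysplastic syndromes (MDS) free time is defined as the time from the first dose of IP to the first occurrence of MDS". Secondary-malignancy-free time is built the same way. SAP Section 9.7 plans Kaplan-Meier curves and hazard ratios for both, and for the two corresponding free-survival times.

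On follow-up, SAP Section 3.1 says: "During the LTFU period, all subjects will be followed by phone or in clinic every 12 weeks". This continues to the end-of-study visit.

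**The concern.** The three branches are consistent for death. Nobody can be known alive in a month after the month of death, so such a record must contain an error.

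The same reasoning fails for MDS or a second cancer. A subject diagnosed in one month and contacted alive in later months is the normal case. The SAP labels that record an error and gives it no date, although the month and year are known.

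MDS and secondary malignancies are listed safety endpoints, and finding them is a stated purpose of long-term follow-up. Events are likely to be few, so a single undated event can matter to the event-free curves.

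**Working it through.** The SAP states no figure on this point, so there is none to reproduce. The check applies the rule as written.

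**1. Does follow-up stop at diagnosis?** No. SAP Section 3.1 follows all subjects every 12 weeks to end of study. Protocol Section 5.3.2 puts study duration at about 14 to 50 months per subject. The reasons for removal from the study in Protocol Section 8.2.2 are sponsor decision, withdrawn consent, death and loss to follow-up. A diagnosis is not among them. Later contact is therefore the expected course.

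**2. Worked case (illustrative dates).** First dose 15 Jan 2021; MDS onset Sep 2021, day missing.

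| Last contact | Death/malignancy/MDS block | General start-date table, stop date missing |
|---|---|---|
| 20 Jun 2022 | data error, no date | 1 Sep 2021 |
| 25 Sep 2021 | 26 Sep 2021 | 1 Sep 2021 |

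Both rules stand in Appendix B and give different answers for the same record. SAP Section 5 identifies MDS by a MedDRA query on coded events, so both could be thought to apply. The SAP does not reconcile them.

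**3. What is discarded.** By the SAP formula, MDS-free time is onset date minus first dose date plus 1. Onset on 1 Sep 2021 gives 229 + 1 = 230 days, and onset on 30 Sep 2021 gives 258 + 1 = 259 days. The known month fixes the event time to within 29 days, yet the rule assigns no time. If the subject were instead censored at last contact on 20 Jun 2022, the record would read 521 + 1 = 522 event-free days.

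**4. How often the branch applies, given a missing day.** Assume that first dose and last contact both fall on the 15th and that onset is equally likely on any day between them. Only the 15 onset days in the month of last contact escape the data-error branch. The share caught is (N − 15)/N, where N is the number of days from first dose to last contact, both included.

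| Follow-up (months) | N | Share undated |
|---|---|---|
| 3 | 91 | 76/91 = 84% |
| 6 | 182 | 167/182 = 92% |
| 12 | 366 | 351/366 = 96% |
| 14 | 425 | 410/425 = 96% |
| 24 | 731 | 716/731 = 98% |
| 50 | 1521 | 1506/1521 = 99% |

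These shares are conditional on the day being missing. They say nothing about how often that happens. Onsets concentrated late in follow-up, or death soon after diagnosis, would lower them.

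**5. Handling of an undated event.** In SAP Section 5, censoring for MDS-free and malignancy-free time applies to subjects without the event. A subject with a known but undated event is neither an event with a time nor a stated censored case.

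**6. Same-month branch.** Onset is placed on the day after the subject was last known alive, or at end of study if that is earlier. This is also illogical for a non-fatal event, but the error is under one month (at most 25 days in the case above, if true onset was 1 Sep).

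**The case against.** The strongest reply is that the trigger should be rare and the effect limited. Protocol Appendix 4 requires onset dates for adverse events, gives invasive or malignant cancers as examples of serious events, and makes the start date mandatory on the contingency form. Serious events are reported within 24 hours through end of study. Long-term follow-up asks about these diagnoses directly, and a data-error flag could prompt a site query. Protocol Section 3.3.3.6 cites latencies of 3 to 5 and 5 to 7 years for treatment-related myeloid disease, against 14 to 50 months on study, so MDS events should be few. These analyses also lie outside the testing hierarchy.

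Most of this stands as a limit on size. It does not defend the rule. The SAP does not say that the flag leads to a query, and a query cannot always recover a day. Contacts may be by phone, so a report giving only month and year is plausible.

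Two stronger readings are tempting, and the documents do not support them:

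- A reader might infer that the reported incidence of MDS or malignancy falls. It does not: the number and percentage of subjects with an event in SAP Section 9.7 need no onset day.
- A reader might infer that the SAP drops these subjects or censors them as event-free, biasing the comparison toward no risk. The SAP specifies neither. The rule is the same in both arms, so a lost romiplostim event would lower the hazard ratio and a lost placebo event would raise it.

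**Conclusion.** The rule is wrong as written for MDS and secondary-malignancy onset, and it conflicts with the general start-date table in the same appendix.

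An affected event has no usable time in the MDS-free and malignancy-free analyses, and its handling is undefined. Whether the subject is dropped or censored, the event is lost from those curves. In the free-survival analyses it is lost or replaced by a later death. Lost events make the event-free curves look better than they are; the direction for the hazard ratio depends on which arm loses the event.

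The problem is confined to onsets with month and year known and the day missing. Given a missing day, about 96% to 99% would go undated over 14 to 50 months of follow-up, under the uniform-onset assumption. The documents give neither the expected number of events nor the frequency of missing days, so the number of affected records is unknown and probably small. The tabulated counts and percentages, the primary endpoint and alpha are not affected. The correction should be made because the rule fails in the ordinary case and costs little to repair.

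**What to change.** In SAP Appendix B, restrict the data-error and day-after-last-contact branches to death dates. For MDS and secondary-malignancy onset with known month and year, impute the first of the month, or the first IP dose date when onset falls in the first-dose month, and in either case no later than death or last contact. This agrees with the general start-date table and removes the conflict between the two rules.

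The cost is a change of SAP wording and a small change to the derivation code, made before database lock. No new data collection or method is needed.
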